#### **7.4.3. Sequential Organ Failure Assessment Score**

##### **7.4.3.1. Summary and Analysis of SOFA Score**

The change from baseline to Day 3, 5, 8, 11, 15, and 29 in SOFA score (see [Appendix C](#)) will be summarized descriptively by treatment group.

Participants released from the hospital who are lost to follow-up will be considered missing with regards to numeric summaries of this endpoint. Missing intermediate days between observations will be imputed to the worst (highest) score from the 2 nonmissing observations.

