- P All medications, procedures, and significant non-drug therapies administered from randomization through Day 29 must be recorded on the appropriate eCRF. Additionally, antivirals and therapeutic agents administered for SaRS-CoV-2 infection/COVID-19 infection and treatments for COVID-19 pneumonia/ARDS administered within 14 days of randomization must also be recorded. If participant is discharged from the hospital, the scheduled assessments may be performed via telephone.
- ^q The SOFA score is to be determined per Appendix C. Not required after discharge from the ICU. SpO₂ method for calculating respiratory score may be used if arterial blood gases were not performed on corresponding assessment day.
- ^r In-hospital outcomes will be collected on eCRFs as outlined in Section 9.3.5.

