9.3.4. Sequential Organ Failure Assessment Score

The SOFA score (Appendix C) is a scoring system to determine the extent of a person's organ function or rate of failure. The score is based on 6 different scores, 1 each for the respiratory, cardiovascular, hepatic, coagulation, renal, and neurological systems. The screening/Day 1 assessment should be based on data collected closest to (but also prior to) randomization. Each subsequent day should use the worst value for each parameter in the preceding 24-hour period.

At each required timepoint, the SOFA score will be calculated by the investigative site and recorded in the appropriate eCRF. The SOFA score assessments are no longer required after discharge from the ICU.

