**Table 1: Objectives and Endpoints (Continued)**

Objectives	Endpoints
To evaluate the efficacy of ruxolitinib 5 mg BID + SoC therapy and ruxolitinib 15 mg BID + SoC therapy compared with placebo + SoC therapy on change from baseline SOFA score in participants with COVID-19–associated ARDS who require mechanical ventilation.	Change from baseline to Day 3, 5, 8, 11, 15, and 29 in SOFA score.
To evaluate the safety of ruxolitinib 5 mg BID + SoC therapy and ruxolitinib 15 mg BID + SoC therapy compared with placebo + SoC therapy in the treatment of participants with COVID-19–associated ARDS who require mechanical ventilation.	Number and proportion of participants with treatment-related side effects (as assessed by CTCAE v5.0) and SAEs; includes clinically significant changes in laboratory measures and vital signs.
Exploratory	
To evaluate the efficacy of ruxolitinib + SoC therapy compared with placebo + SoC therapy in proportion of participants requiring IL-6, IL-1, GM-CSF, or JAK-directed therapies.	Proportion of participants requiring treatments with IL-6, IL-6RA, IL-1RA, IL-1 beta, GM-CSF, BTK, or JAK directed therapies by Day 15 and by Day 29.
To evaluate ruxolitinib + SoC therapy compared with placebo + SoC therapy on change in inflammatory markers (when available).	Change from baseline to Day 15 and to Day 29 in the following clinical chemistry measurements: 
 
• Serum ferritin
 
• CRP
 
• D-dimer
 
• Procalcitonin
 
• IL-6
 

To evaluate ruxolitinib + SoC therapy compared with placebo + SoC therapy on change in COVID-19 virologic and serologic parameters.	Change from baseline to Day 15 and Day 29 in viral load and anti–SARS-CoV-2-antibody titer.

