### 7.4.2. COVID-19 9-Point Ordinal Scale

The COVID-19 9-Point Ordinal Scale (see [Appendix B](#)) will be tabulated by study day, ordinal category, and treatment group. Participants with missing values due to death will be imputed to have Category 8 (death). Participants released from the hospital that are lost to follow-up will be considered missing with regards to this endpoint. Missing intermediate days between observations will be imputed to the worst (highest) category from the 2 nonmissing observations.

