##### **7.4.3.2. Summary and Analysis of SOFA Score Components**

Individual scoring of organ systems (respiratory, nervous system, cardiovascular, liver, coagulation, and kidneys) will be tabulated. Individual organ system scores by scheduled Study Days 3, 5, 8, 11, 15, and 29 will be compared using the Cochran-Mantel-Haenszel test stratified by baseline organ system score (0, 1, 2, 3, or 4). Participants who have died will be imputed to the worst value (4) of the component. Such comparisons will be for exploratory purposes to determine if the response is being driven by a subset of the components of the SOFA score.

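### By the later visits, change in total SOFA mainly describes participants alive and still in the ICU, because SAP 7.4.3.1 gives no value for death or ICU discharge

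*SAP*

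**What the plan says.** The endpoint in SAP Table 1 is "Change from baseline to Day 3, 5, 8, 11, 15, and 29 in SOFA score". SAP 5.3.2 assigns all efficacy analyses to the ITT population, and Appendix A lists the SOFA tables (2.2.6.1 to 2.2.6.3) as ITT. Under SAP 7.4.3.1 the total score "will be summarized descriptively by treatment group"; no test or model is planned for it.

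On collection, Protocol 9.3.4 says "The SOFA score assessments are no longer required after discharge from the ICU", and footnote q to the Schedule of Activities (Protocol Table 3) repeats it: "The SOFA score is to be determined per Appendix C. Not required after discharge from the ICU".

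For missing total scores, SAP 7.4.3.1 has two rules and no others. The first covers people who leave hospital and cannot then be traced: "Participants released from the hospital who are lost to follow-up will be considered missing with regards to numeric summaries of this endpoint". The second covers gaps with a score on either side, and takes the worse of the two scores.

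For the six organ components, SAP 7.4.3.2 plans a Cochran-Mantel-Haenszel comparison at the same visits, stratified by baseline organ score and labelled exploratory. Here "Participants who have died will be imputed to the worst value (4) of the component". Nothing is said about participants who have left the ICU.

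Elsewhere the SAP does place deaths: in the worst category of the 9-point scale (7.4.2) and at zero event-free days (7.4.1).

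**The concern.** Death and ICU discharge are both outcomes that the drug is meant to change. A mean taken only over participants who have done neither compares subsets selected after randomization, and the selection can differ by arm. A drug that keeps very sick participants alive in the ICU, or moves recovering ones out sooner, alters who is left to be scored. The by-arm tables will still be read against an objective that asks for efficacy versus placebo.

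The component analysis has a further problem. It keeps the worst outcome at a fixed score of 4 and has no place for the good outcome of leaving the ICU.

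**Working it through.** The documents give no sample size, standard deviation or expected value for SOFA, so there is no SOFA figure of the plan's to reproduce. The check has four steps.

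**1. Which rule reaches which participant**

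| Status at a SOFA visit | Total score (7.4.3.1) | Components (7.4.3.2) |
|---|---|---|
| Alive, in ICU | Observed | Observed |
| Alive, out of ICU, followed | No rule | No rule |
| Out of ICU, later scored again | Gap rule: worse of the two observations | No rule stated |
| Out of hospital, lost | Missing | No rule stated |
| Dead | No rule | 4 |

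The gap rule needs an observation on each side. It cannot reach a death, and it reaches an ICU leaver only if that person is scored again. It then fills the time outside the ICU with the worse of the two scores, which may be the one before discharge or the one after.

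**2. Ceiling on the number with a Day 29 total**

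Inputs: 211 participants (SAP 3.3), 2:2:1 allocation (SAP 3.1), 60% placebo and 40% ruxolitinib mortality (SAP 3.3). An exact split gives 211/5 = 42.2, so about 42 placebo and 84 per ruxolitinib arm.

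Ceiling = n × (1 − mortality)

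- Placebo: 42 × 0.40 = 16.8, about 17 of 42
- Each ruxolitinib arm: 84 × 0.60 = 50.4, about 50 of 84

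ICU discharge lowers these further. The documents give no discharge rate, so I assume that 25%, 50% or 75% of survivors are out of the ICU by Day 29.

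Number scored = n × (1 − mortality) × (1 − share out)

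| Share of survivors out | Placebo (of 42) | Each ruxolitinib arm (of 84) |
|---|---|---|
| 25% | 12.6 | 37.8 |
| 50% | 8.4 | 25.2 |
| 75% | 4.2 | 12.6 |

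**3. The asymmetry in the components**

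Suppose mortality is 50% in both arms (an assumption) and ICU leavers have no value. The share of analysed participants scored 4 because of death is 0.5 / [0.5 + 0.5 × (1 − share out)].

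- 40% of survivors out: 0.5 / 0.80 = 62.5%
- 70% of survivors out: 0.5 / 0.65 = 76.9%

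At equal mortality, the arm with faster ICU discharge shows more 4s.

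**4. Direction of the bias in the total**

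Take assumed Day 29 states, none of them from the documents. Placebo: 60% dead, 20% out of ICU, 12% in ICU with change +1, 8% in ICU with change −4. Ruxolitinib: 40%, 34%, 20% and 6%.

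- Available-case mean, placebo: (12 × 1 − 8 × 4) / 20 = −1.0
- Available-case mean, ruxolitinib: (20 × 1 − 6 × 4) / 26 = −0.15

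Ruxolitinib looks worse. Now score death as 24 and out of ICU as 0, with baseline 9, for illustration only:

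- Placebo: 0.60 × 15 − 0.20 × 9 + 0.12 × 1 − 0.08 × 4 = +7.0
- Ruxolitinib: 0.40 × 15 − 0.34 × 9 + 0.20 × 1 − 0.06 × 4 = +2.9

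The sign reverses, but the reversal rests on the assumed mix within the ICU: 8/20 = 40% of scored placebo participants have −4, against 6/26 = 23% on ruxolitinib. Give both arms the 60:40 mix and each mean is 0.6 × 1 − 0.4 × 4 = −1.0, with no difference.

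A separate simulation derived the mix from a severity model. Baseline was 9, change was −2 + 3 × severity plus noise with SD 2, the sickest died and the best survivors left the ICU. Mortality was 60% against 40%, with no direct effect on SOFA. With equal discharge shares of 0%, 30% and 50% of survivors, ruxolitinib looked 0.96, 1.10 and 1.22 points worse on available cases. With 30% against 60% discharged it looked 1.84 points worse. Scoring death as 24 and out of ICU as 2 made it 3.4 to 4.1 points better in the same four settings.

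**The case against.** The strongest reply is that this is an unstated rule in a descriptive table. SOFA after ICU discharge is not required, which is different from not collected. The SAP is silent on deaths in the total; it does not exclude them, and a programmer could sum the component rule to 6 × 4 = 24. The total carries no test and the components are exploratory. Mortality, ICU-free days and the 9-point scale all count death, and ICU-free days count ICU discharge directly. SAP 5.1 requires the number of observations, so the shrinking denominators will be visible.

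Most of this is fair, and it limits the importance of the point. It does not remove it. Ward scores would be patchy: after screening, blood gases are scheduled only during ventilation or with an arterial line, and visits after hospital discharge may be by telephone. Silence on death leaves two codings that can give opposite pictures. If deaths are coded 24 while ICU leavers stay missing, the total takes on the components' asymmetry. A bare count of observations does not separate the dead from the recovered.

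A composite also has a real weakness. In the worked example its 4.1-point advantage is 0.20 × 15 = 3.0 from mortality plus 0.14 × 9 = 1.26 from ICU discharge, less 0.16 from the participants actually scored. It largely repeats other endpoints. A literal 0 outside the ICU has no basis in Appendix C, which scores measured values.

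**Conclusion.** The point holds as a gap in the rules that affects how the later visits can be read. From about Day 8 the planned change in total SOFA mainly describes participants alive and assessed in the ICU, and it does not support an ITT comparison. Days 3 and 5 are less affected, since everyone enters intubated. The ceilings of about 17 of 42 and 50 of 84 at Day 29 rest on the plan's mortality rates, an exact 2:2:1 split and deaths having no score. Anything below them rests on an assumed ICU discharge rate.

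A reader might infer that the endpoint cannot address its objective at any visit, or that an effective drug would look worse on it. The documents support neither. The early visits are usable, and both the direction and the size of the bias depend on who remains in the ICU. A sign reversal is possible, not shown. The component asymmetry is firmer: given the stated death rule and no value for ICU leavers, faster discharge can worsen an arm's distribution.

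**What to change.** Before unblinding, amend SAP 7.4.3.1 and 7.4.3.2 as follows:

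- At each SOFA day, use a rank-based summary or comparison in all ITT participants with known status. Rank death worst, consistent with the component rule, and alive and out of the ICU best, as a rank and not as a measured score of 0.
- As a sensitivity analysis, carry the last ICU score forward for participants alive and out of the ICU.
- Do not apply the worst-of-two-observations rule across an interval spent out of the ICU.
- In Tables 2.2.6.1 to 2.2.6.3, report the numbers dead, out of the ICU and scored, by arm and day. Label the available-case mean change as conditional on being alive and assessed.

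The cost is SAP wording and table programming. Death dates are collected (Protocol 9.3.1) and ICU-free days are derived by calendar day (SAP 7.4.1), so no new data should be needed; confirm that ICU status can be recovered for each SOFA day. The composite is less familiar than a raw SOFA change and partly overlaps with mortality and ICU-free days, so keep the conditional summary beside it.

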##### **7.4.3.2. Summary and Analysis of SOFA Score Components**

Individual scoring of organ systems (respiratory, nervous system, cardiovascular, liver, coagulation, and kidneys) will be tabulated. Individual organ system scores by scheduled Study Days 3, 5, 8, 11, 15, and 29 will be compared using the Cochran-Mantel-Haenszel test stratified by baseline organ system score (0, 1, 2, 3, or 4). Participants who have died will be imputed to the worst value (4) of the component. Such comparisons will be for exploratory purposes to determine if the response is being driven by a subset of the components of the SOFA score.

#### **7.5. Analysis of Exploratory Efficacy Variables**

##### **7.5.1. Participants Receiving IL-6, IL-6R, IL-1RA, IL-1 $\beta$ , GM-CSF, BTK, or JAK-Directed Therapies**

The number of participants receiving IL-6, IL-6R, IL-1RA, IL-1 $\beta$ , GM-CSF, BTK, or JAK-directed therapies by Day 15 and by Day 29 will be summarized for the safety population. The list of such therapies will include, but is not limited to, the following: tocilizumab, canakinumab, anakinra, or sarilumab. A blinded review of concomitant medications will be performed to identify any agents meeting this criteria prior to unblinding of the clinical team.

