12. STATISTICS

12.1. Sample Size Determination

The primary endpoint of this study is the proportion of participants who die on or prior to Day 29. Participants will be randomized at a 2:2:1 (5 mg BID ruxolitinib:15 mg BID ruxolitinib:placebo) ratio. The primary endpoint will be tested using a logistic regression mixed model including treatment group, ARDS severity (mild/moderate [PaO₂/FiO₂ > 100 to \leq 300] vs severe [PaO₂/FiO₂ \leq 100]), and gender as covariates and investigational site as a random (intercept) effect. The Wald test for the treatment regression coefficient will test the primary endpoint. Individual comparisons between placebo and ruxolitinib treatment arms will be performed in a pairwise fashion (placebo vs 5 mg BID and placebo vs 15 mg BID), with alpha-control accomplished using a Dunnett's procedure. Based on the expected correlation between the 2 statistical tests of 2/3, the adjusted nominal p-values for each treatment group is approximately 0.01436968.

Assuming a 40% mortality rate for ruxolitinib vs 60%, a sample size for a pairwise comparison of 100 placebo and 200 ruxolitinib participants (with 500 participants total) will achieve approximately 83% power to detect a statistically significant difference with a nominal 1-sided Type I error of 1.436968%. Estimated power for various scenarios, based on a simulation study of 1000 study replications, are provided in Table 8.

	Mortality Rates			Probability to Reject H ₀ for		
PLB	5 mg BID	15 mg BID	5 mg BID	15 mg BID	Either RUX	
60%	60%	60%	0.015	0.016	0.027	
60%	60%	40%	0.012	0.873	0.873	
60%	50%	40%	0.268	0.865	0.866	
60%	40%	40%	0.868	0.872	0.940	
60%	40%	30%	0.861	0.998	0.998	

Table 8:Simulation Estimates for Power and Type 1 Error for Various Mortality
Rates

Note: For the simulation, investigational site was drawn from a integer uniform distribution (1, 2, ..., 10) and probability (ARDS severe) = 0.5, fitting a mixed logistic regression model with no direct effects for the ARDS severity or site.

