12.4.3. Exploratory Efficacy Analyses

Change from baseline to Day 15 and Day 29 in serum ferritin, C-reactive protein (CRP), D-dimer, IL-6, and viral load will be summarized by treatment arm. Additional details will be provided in the Statistical Analysis Plan.

Exploratory endpoints will be summarized descriptively using ITT population.

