#### **5.3.2. Intent-to-Treat Population**

All participants who are randomized will constitute the ITT population. Treatment groups for this population will be defined according to the treatment assignment at the time of randomization regardless of the actual study drug the participant might take during his/her participation in the study.

The ITT population will be used for the summary of demographics, baseline characteristics, participant disposition, and analyses of all efficacy data.

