#### **5.3.4. Safety Population**

The safety population will include all participants who received at least 1 dose of ruxolitinib/placebo. Treatment groups for this population will be determined according to the actual treatment the participant received regardless of assigned study drug treatment.

All safety analyses will be conducted using the safety population.

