### 11.1. Changes to Protocol-Defined Analyses

#### 11.1.1. Original to Amendment 1

- The analysis for time to improvement from baseline category to earliest 1-point improvement in the ordinal scale was restated as time to improvement from baseline category to earliest improvement of any kind.
- After FDA feedback, the initial plan for treatment groups continued beyond rejection of their specific null hypothesis at the efficacy interim analysis where final reported p-values would be based on the highest level of significance achieved, either at the interim or final analysis, was modified to report p-values from the final analysis at final reporting.
- Gender was removed from analyses of the primary and secondary endpoints and added as a sensitivity analysis for the primary endpoint.

#### 11.1.2. Amendment 1 to Amendment 2

- The weekly overall survival futility analysis was replaced by a conditional power analysis to occur after approximately every 50 participants enrolled have at least 2 weeks of follow-up.
- The reference level of ARDS severity was changed to be mild/moderate instead of severe.

#### 11.1.3. Amendment 2 to Amendment 3

- Section 3.2, Section 3.3, Section 5.1, Section 7.3.1, Section 7.3.3, Section 10, Appendix A – The interim analysis and conditional power analysis were removed. The only remaining analysis will be the final analysis.
- Section 3.2, Section 5.3.3, Section 5.3.5, Section 7.2, Section 7.5.1, Section 7.5.2, Section 7.5.3, Appendix A – The alpha control strategy for the primary efficacy analysis was changed. The definition of the PP population was modified, and the PD-evaluable population was removed. Any planned analyses that previously used the PD-evaluable population will use the safety population instead.

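### The exploratory rescue-therapy endpoint is summarised in the safety population although Protocol 12.4.3 and SAP 5.3.2 call for ITT, and, as a separate point, its bare count does not show deaths without rescue.

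*SAP*

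**What the plan says.** The endpoint in SAP Table 1 is a simple proportion: "Proportion of participants requiring treatments with IL-6, IL-6RA, IL-1RA" and the other listed classes, by Day 15 and by Day 29. The matching objective, in Protocol Table 4 and SAP Table 1, is worded as one of efficacy. SAP 7.5.1 falls under the exploratory efficacy variables and plans that participants receiving such "therapies by Day 15 and by Day 29 will be summarized for the safety population". Table 2.3.1 in SAP Appendix A also names the safety population. Neither place gives a rule for deaths, a test or a model.

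On population, Protocol 12.4.3 states: "Exploratory endpoints will be summarized descriptively using ITT population". SAP 5.3.2 states: "The ITT population will be used for the summary of demographics, baseline characteristics, participant disposition, and analyses of all efficacy data". SAP 5.3.4 defines the alternative: "The safety population will include all participants who received at least 1 dose of ruxolitinib/placebo", with groups formed by actual treatment. SAP 11.1.3 lists Section 7.5.1 in a change entry that says: "Any planned analyses that previously used the PD-evaluable population will use the safety population instead".

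**The concern.** There are two separate points.

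**Population.** An endpoint with an efficacy objective is analysed in treated participants by treatment received, against a general rule in each document. Receipt of a concomitant drug needs no post-treatment pharmacodynamic sample, so nothing about this endpoint explains why it was tied to the PD-evaluable population or to its replacement.

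**Deaths.** A participant who dies without rescue stays in the denominator and is not counted as an event. Death ends the opportunity to receive rescue. Most of the listed classes are also prohibited until study treatment stops (Protocol 7.2.2), so receipt depends partly on surviving past discontinuation. If ruxolitinib lowers mortality, its arm has more time in which rescue can occur. A reader of Table 2.3.1 alone could take a survival benefit for a greater need for rescue.

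**Working it through.** **Population.** Set side by side, Protocol 12.4.3 (exploratory endpoints in ITT) and SAP 5.3.2 (all efficacy data in ITT) conflict with SAP 7.5.1 and Table 2.3.1 (safety). SAP 11.1.3 explains where the safety population came from but cites neither ITT statement. To gauge size, assume a fraction u of an arm is untreated and unrescued. An ITT proportion p then becomes p/(1 − u) in the safety population. With p = 10% and u = 1%: 0.10/0.99 − 0.10 = 0.1 points. With p = 20% and u = 5%: 0.20/0.95 − 0.20 = 1.1 points. Any effect of regrouping by treatment received is not quantified here.

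**Deaths: inputs.** The plan states no figure for rescue. Mortality comes from Protocol 12.1: "Assuming a 40% mortality rate for ruxolitinib vs 60%, a sample size for a pairwise comparison of 100 placebo and 200 ruxolitinib participants". As a check on those inputs, the power at 1-sided 0.01436968 is 83.7% (continuity-corrected) or 83.2% (Fisher), against about 83% stated. The uncorrected 86.6% lies within the 0.861 to 0.873 simulated for 60% vs 40% in Protocol Table 8.

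**Model (assumed).** Hazards are constant over 28 days, and the daily rescue hazard h is equal in both arms, so the drug has no effect on rescue.

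- Death hazard d = −ln(1 − mortality)/28. Placebo: −ln(0.4)/28 = 0.0327. Ruxolitinib: −ln(0.6)/28 = 0.0182.
- Crude proportion rescued by Day 29 = h/(h + d) × [1 − exp(−28(h + d))].
- Placebo at h = 0.01: 0.01/0.0427 × (1 − exp(−1.196)) = 0.234 × 0.698 = 16.3%.
- Ruxolitinib at h = 0.01: 0.01/0.0282 × (1 − exp(−0.791)) = 0.354 × 0.547 = 19.4%.

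| Assumed h per day | Placebo | Ruxolitinib | Excess (points) |
|---|---|---|---|
| 0.005 | 8.6% | 10.3% | 1.6 |
| 0.01 | 16.3% | 19.4% | 3.1 |
| 0.02 | 29.3% | 34.4% | 5.1 |

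(The excess is taken before rounding.)

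For assumed rescue rates in the absence of death of 5% to 30% over 28 days, the Day 29 ratio is 1.18 to 1.19. By Day 15 it is about 1.10. With ruxolitinib mortality of 50% instead of 40%, the Day 29 ratio is about 1.10; with 30% it is 1.26 to 1.28. At 60% vs 40%, the drug would have to cut the rescue hazard by about 17% just to show equal crude proportions. A true 15% cut at h = 0.01 shows as 16.3% vs 16.8%.

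**Against sampling noise.** SAP 3.3 gives 211 participants. At 2:2:1 that is about 42 placebo and 84 per ruxolitinib arm. The 95% half-width for 16.3% vs 19.4% is 1.96 × √(0.163 × 0.837/42 + 0.194 × 0.806/84) = 1.96 × 0.071, or about 14 points. The artefact is 3.1 points.

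**Would a death-or-rescue composite help?** Composite = 1 − exp(−28(h + d)). With equal h = 0.01 it is 69.8% placebo vs 54.7% ruxolitinib, a gap of 15.1 points when the drug has no effect on rescue. If ruxolitinib doubles the hazard to 0.02, its composite is 1 − exp(−28 × 0.0382) = 65.7%, still below the placebo 69.8%.

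**The case against.** Taken literally, the endpoint is a proportion by a fixed day. With complete follow-up, the observed proportion is a legitimate cumulative incidence with death as a competing event. Calling it biased presupposes that the rescue hazard is the target. This stands: the count is valid for what it measures, and only its reading as need for rescue is at risk. For the same reason, relabelling it a competing-risks cumulative incidence would change nothing.

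The SAP writes no success or failure coding for deaths. A reader might infer that it deliberately scores early deaths as successes, but the text is silent and the result is only the default of a count. The explicit death rules elsewhere (ordinal scale, event-free days, SOFA components) belong to measures on which death has a natural worst value. The total SOFA summary in SAP 7.4.3.1 has no death rule either, so there is no uniform rule that 7.5.1 breaks.

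The endpoint is exploratory and, under Protocol 12.4.3, descriptive. Mortality by arm is the primary table, and deaths and the listed therapies are both listed by participant. A reader might infer that the objective cannot be answered; the documents do not support that, because the components are reported, only not together.

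The population change is recorded in SAP 11.1.3. That answers any suggestion that it was unannounced, but it does not reconcile 7.5.1 with Protocol 12.4.3 or SAP 5.3.2.

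**Conclusion.** Both points hold, at low weight, and they are independent. A reader might infer that using the safety population is what makes a life-prolonging drug look worse on rescue. It is not: that artefact comes entirely from the crude count and would be the same in ITT.

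The population conflict is a consistency defect. Its numerical effect is probably small, 0.1 to 1.1 points if 1% to 5% of an arm is untreated and unrescued. SAP 7.5.2 and 7.5.3 share it.

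The survival distortion is about 1.2-fold at Day 29, or 1.6 to 5.1 points for daily rescue hazards of 0.005 to 0.02. This rests on constant and equal rescue hazards, on assumed rescue rates, and on the planning mortality being realised. A constant hazard from Day 1 also ignores the restriction on these agents during study treatment. With no mortality difference there is no distortion, and at 211 participants it lies within noise. No confirmatory conclusion is affected.

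**What to change.** In SAP 7.5.1 and Table 2.3.1, use the ITT population as randomized. For Day 15 and for Day 29, report by arm:

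- participants who started a listed therapy after randomization;
- participants who died without it;
- participants alive without it.

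Show anyone whose status is unknown as unknown. State that the rescue row is read only beside the deaths row. Do not present a death-or-rescue composite as the efficacy summary for rescue, because mortality dominates it and it can favour ruxolitinib even if rescue increases. In SAP 11.1.3, address Protocol 12.4.3 and SAP 5.3.2 explicitly, and settle 7.5.2 and 7.5.3 in the same edit.

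The cost is a few lines of SAP text and one or two extra table rows. Death dates (Protocol 9.3.1) and medications from randomization through Day 29 (Protocol 7.2.1) are already collected. The downside is that randomized participants who were never treated enter the denominator.
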